having a singleton pregnancy. The midwife will ask the woman if she is willing to participate in the IRIS study and if so, the midwife will ask her to sign the consent form. The form asks the woman's permission for using her personal data for merging data, for collecting detailed information from the woman's and her baby's client records, and for approaching her in the context of future sub-studies. An extra consent form will be added among the subsample of women who will fill in questionnaires. Consent forms will contain name, address, postal code, telephone number, and email and will be kept separate from other data files in a secure place.

Inclusion criteria: receiving

Women who do not have had a dating US will only be included if they have a reliable estimated data of delivery (EDD) based on the first day of their last menstrual period.

The NVOG guideline on US dating of pregnancy will be used for estimation of the EDD.

CONTROL AND INTERVENTION US STRATEGIES

Women in both US strategies will receive routine care as follows:

- Standardised SFH measurement
- Information about life style factors that may influence foetal growth, such as smoking, use of alcohol and drugs, and labour circumstances.
- Advise to report a reduction in fetal movements.
- US examinations on indication

Subsequent protocolised management will be according to the IRIS consensus-based protocol (to be developed in sub-study A).

Intervention US strategy

Additionally, two routine third trimester US examinations will be performed, one between 28 and 30 weeks and one 6 weeks after the first US. By performing two US examinations the growth pattern can be monitored. If a baby does not follow the expected curve, this may indicate a lack of growth even before the abdominal circumference or the estimated fetal weight is low. Subsequent protocolised management will be accomplished according to the IRIS consensus based guidelines.

PRIMARY OUTCOME - SEVERE ADVERSE PERINATAL OUTCOME

The primary clinical outcome is the occurrence of any severe adverse perinatal outcome up to 7 days after birth (yes/no). It concerns a dichotomous composite measure with 'yes' being defined as the presence of one or more of the following:

1. Antepartum, intrapartum or neonatal death occurring from 28 weeks gestation
2. Apgar score below 4 at 5 minutes after birth;
3. Coma, stupor or decreased response to pain;
4. Asphyxia, defined as cord blood arterial base excess of less than minus 12;

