5. Neonatal seizures defined as clonic movements which cannot be stopped by holding the limb, occurring on two or more occasions before 72 hours of age;
6. Assisted ventilation for more than 24 hours via endotracheal tube initiated within 72 hours after birth;
7. Septicaemia, ascertained by a positive blood culture;
8. Meningitis, ascertained by positive cerebrospinal fluid culture;

9. Bronchopulmonary dysplasia (BPD), defined as need for oxygen at a postnatal gestational age from 36 completed weeks as well as an X-ray compatible with BPD;
10. Intraventricular hemorrhage, defined as grade 3 or 4 and diagnosed by cranial US or at autopsy;
11. Cystic periventricular leukomalacia (PVL), diagnosed by cranial US or at autopsy showing periventricular cystic changes in the white matter excluding subependymal and choroid plexus cysts;
12. Necrotizing enterocolitis, defined as either perforation of intestine, pneumatosis intestinalis or air in the portal vein, diagnosed by X-ray, surgery, or at autopsy;

Cord blood arterial base excess was chosen as an indicator of asphyxia because, unlike pH, it is linearly related to the degree of metabolic acidosis which is a better indicator of asphyxia than measures of respiratory acidosis [Ross & Gala, 2002]. There was some discussion in the expert and project group on the use of Apgar scores in the composite outcome. Apgar score in itself is not comparable to the other outcomes, which are more predictive of long term severe adverse outcomes. However, in the Netherlands, a quarter of all women still give birth at home. Suspected SGA is a reason for referral to specialist care and routine US may lead to more SGA babies being born in hospital. Nevertheless, unexpected poor outcomes may occur at home and blood gases immediately after birth will then not be available. In hospital too, cord blood samples may be forgotten or go missing. We have chosen a low cutoff point for Apgar score at five minutes (below 4) in which case most babies will have other adverse outcomes as well. In a recent Dutch RCT on the management of pregnancies complicated by SGA, Apgar scores were also part of the composite outcome [Boers et al., 2010]. Low birth weight is not part of the primary outcome because this is not a measure of morbidity but rather a factor that is associated with morbidity such as respiratory problems. Also, premature labour may sometimes be induced to prevent stillbirth even though prematurity is associated with low birth weight.

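### The asphyxia component of the primary composite needs a cord gas, and routine ultrasound may change who has one, so its ascertainment may differ by strategy and bias against routine ultrasound

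*Protocol*

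**What the plan says.** The protocol section on the primary clinical outcome lists twelve components: "It concerns a dichotomous composite measure with 'yes' being defined as the presence of one or more of the following". Component 4 is "Asphyxia, defined as cord blood arterial base excess of less than minus 12". It requires no clinical sign, and no alternative criterion is given for a baby without a gas.

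The rationale below the list recognises the difficulty. It notes that "in the Netherlands, a quarter of all women still give birth at home". On the effect of the intervention it says: "Suspected SGA is a reason for referral to specialist care and routine US may lead to more SGA babies being born in hospital". On home births it says that "unexpected poor outcomes may occur at home and blood gases immediately after birth will then not be available", and it adds that hospital samples can also be missed or lost. The response is to keep a 5-minute Apgar score below 4 in the composite, "in which case most babies will have other adverse outcomes as well".

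Under Secondary outcomes, the elements of the composite are to be reported singly, as is place of birth (home or hospital) in primary care. Under Data collection, the hospital record review of outcomes covers babies referred for neonatal admission and babies whom the databases already flag with a severe adverse outcome.

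**The concern.** Taken together, these statements link strategy to place of birth, and place of birth to whether component 4 can be observed. Consider a baby with base excess below -12, a 5-minute Apgar of 4 or more and no other component. Sampled in hospital, this baby is an event. Born at home, the same baby is not. If routine ultrasound moves some such births into hospital, the intervention strategy gains events through measurement alone.

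The Apgar criterion does not close this gap. By the protocol's own account, most babies who meet it have another adverse outcome anyway, so it mainly picks up babies who are already counted. The record review cannot recover a gas that was never taken. Covariate adjustment and the intention-to-treat and per-protocol analyses do not address the point.

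The direction is predictable: the artefact works against the hypothesised reduction. Because the trial turns on a small absolute difference in a rare outcome, even a few artefactual events reduce power and complicate the reading of a null result.

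**Working it through.** **1. The plan's own figures.** The sample size section gives 1.54% falling to 1.0%, 80% power and a significance level of 0.05, with 13,536 women before clustering. A two-sided comparison of two proportions gives 2 x 6,749 = 13,498, within 0.3% of that figure. With ICC 0.0003 and cluster size 250, the design effect is 1 + 249 x 0.0003 = 1.0747, and 13,536 x 1.0747 = 14,547, as stated. With 7,500 women per strategy the effective number is 7,500 / 1.0747 = 6,979, and power is 81%. Expected events are 7,500 x 0.0154 = about 116 and 7,500 x 0.010 = 75. These figures are not in dispute and serve only as the yardstick.

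**2. Formula for the artefact.**

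Excess = (share of births that move to where gas is taken) x (probability of being sampled) x (probability of base excess below -12 with no other component).

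**3. Inputs.**
- Share that could move: about 10% of women are classified as high risk at a P10 cut-off (section on adverse effects of US screening), and a quarter of women give birth at home (outcome rationale). 0.10 x 0.25 = 0.025. Combining the two assumes that the national home-birth share applies to these women.
- Probability of being sampled: 50-90%. Assumption; the protocol says only that hospital sampling is incomplete.
- Probability of isolated acidosis: 0.5-2%. Assumption. As an average over all births 2% is a high bound, because the whole composite is expected at only 1.54%. Applied to the 75% born outside the home with 90% sampled, it would give 0.75 x 0.90 x 0.02 = 1.35%, leaving 0.19% for everything else.

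**4. Results.**

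| | Low | High |
|---|---|---|
| Product | 0.025 x 0.5 x 0.005 = 0.0000625 | 0.025 x 0.9 x 0.02 = 0.00045 |
| Excess, percentage points | 0.006 | 0.045 |
| Extra events per 7,500 | 0.5 | 3.4 |
| Share of the 0.54-point target | 1.2% | 8.3% |
| Power (81% without the artefact) | 80% | 74% |

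Power here uses 6,979 per arm, with the excess added to the 1.0% intervention rate.

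**5. Sensitivity to the assumptions.** The babies who move are selected for suspected smallness, so acidosis may be commoner among them than on average. If all of the 2.5% move and are sampled, and 10% have isolated acidosis, the excess is 0.025 x 0.10 = 0.25 points. That is 19 events per 7,500, 46% of the target, and power falls to 31%. This extreme rests on an assumed 10% that nothing in the protocol supports. Full cancellation would need 0.54 points, about 40 events, and lies beyond even this case.

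**The case against.** A reader might infer that the protocol expects routine ultrasound to move births in general into hospital, so that the intervention strategy will show more events. The text does not support this. It says that routine ultrasound may have this effect, and only for small babies. Moving a birth does not guarantee a gas, and a true benefit could outweigh the artefact. A shift of 5-10 percentage points of all births would be two to four times the 2.5% that the protocol's own figures suggest.

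The net shift may be smaller than 2.5%. Control women also have standardised fundal height measurement, ultrasound on indication and the same management protocol, so some would be referred anyway. It could be larger if wrongly suspected babies or slow growth add referrals, or if some births outside the home also go unsampled. The protocol gives no figure for either.

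The authors discussed missing gases openly, justified base excess over pH and added a criterion that needs no gas. That is a reasoned trade-off, and it catches the worst cases. Reporting asphyxia and place of birth separately would also reveal an excess of one beside a shift in the other. This stands, so it would be wrong to say that nothing planned bears on the question. But the single-component count carries the same artefact, and neither report gives the composite without isolated acidosis or shows how many babies had a gas.

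Finally, sensitivity analyses are often left to the SAP, which is not shown. Their absence from the protocol is not the point here. The point is that the protocol fixes an outcome definition whose ascertainment can depend on strategy, and answers this with a criterion that covers only part of the gap.

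**Conclusion.** The concern holds as a risk of differential ascertainment in one of the twelve components, with a predictable direction (against routine ultrasound) and an unknown size. On the 2.5% derived from the protocol, with assumed sampling of 50-90% and isolated acidosis of 0.5-2%, it amounts to about 0.006 to 0.045 percentage points, or 1-8% of the target difference. It would be larger if more births move or if acidosis is commoner among those that do. On these figures the artefact would neither cancel the target effect nor, by itself, make routine ultrasound appear harmful. It could cost several points of power and leave a borderline or null result harder to interpret. This is a cheap improvement to the plan; the primary outcome need not be replaced.

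**What to change.** Keep the primary outcome as defined. Prespecify, in the protocol or SAP:

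- a sensitivity analysis of the primary composite, with the same model, in which base excess below -12 without any other component does not count as an event;
- a table of the proportion of births with an arterial cord gas, by strategy and by place of birth;
- a statement that the primary result will be interpreted beside these two.

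The cost is a few sentences, one more run of the primary model, and a tabulation of whether a cord-gas result is on record. The sensitivity analysis will have fewer events and less precision, and it will leave out some true asphyxia. It is a companion to the primary analysis, not a better version of it. Nor does it make the composite wholly independent of setting: septicaemia, meningitis, intraventricular haemorrhage, periventricular leukomalacia and necrotizing enterocolitis still depend on cultures, imaging, surgery or autopsy. It removes only the part that depends on a cord gas.

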DESIGN: A nationwide stepped wedge cluster randomised trial in which primary care midwifery practices will be randomised.

PARTICIPANTS: 15,000 women who receive/continue care in the participating midwifery practice after the 20 week structural ultrasound and who have a singleton pregnancy.

INTERVENTION AND CONTROL STRATEGIES: In all midwifery practices, growth will be monitored using standardised symphysis fundal height (SFH) measurement. In the intervention strategy two routine US examinations will be performed (between 28-30 weeks and 34-36 weeks), while in the control strategy US examination will only be performed when clinically indicated. In both groups the IRIS consensus-based protocol will be followed if intrauterine growth retardation is suspected.

PRIMARY OUTCOMES: The clinical primary outcome is a dichotomous composite measure 'severe adverse perinatal outcome' up to 7 days after birth, including: perinatal death; Apgar score below 4 at 5 minutes after birth; impaired consciousness; need for assisted ventilation for more than 24 hours; asphyxia; septicaemia; meningitis; bronchopulmonary dysplasia; intraventricular haemorrhage; cystic periventricular leukomalacia; neonatal seizures or necrotizing enterocolitis. Also direct and indirect costs are primary outcomes.

SAMPLE SIZE: A total of 15,000 women in 60 midwifery practices; 7,500 women per strategy.

MAIN DATA ANALYSIS AND ECONOMIC EVALUATION: Multivariable logistic regression analyses, taking into account the clustered design. The economic evaluation will consist of a cost-effectiveness and a cost-utility analysis and will be performed from both a health care provider and societal perspective. We will base all primary analyses on intention to treat.

DURATION: 48 months.

Problem definition

DETECTION OF SMALL-FOR-GESTATIONAL-AGE

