Based on PRN data the expected rate of severe adverse perinatal outcome in the study population is 1.54 %. Unfortunately, national or international consensus is lacking on what reduction in severe perinatal outcome is feasible and clinically relevant. The IRIS study group agreed to strive for a reduction from 1.54% to 1.0% in the primary outcome. With 80% power and a significance level of 0.05, we need to include 13,536 women. However, given the clustered design this sample size needs adjustment for dependency of data.

Pagel et al. (2011) note that intra cluster correlation (ICC) estimates for perinatal health outcomes in primary care are scarcely available in literature; most come from hospital-based studies and may therefore not reflect outcomes in the community. To change this situation, the authors estimated the ICC and the coefficient of variation for a range of outcomes using data from five community-based c-RCTs in three low-income countries. In their paper they present five ICCs for neonatal mortality ranging from 0.0003 to 0.002. Additionally, they performed a simulation exercise to investigate the impact of cluster size and number of clusters on the reliability of estimates of the coefficient of variation for rare outcomes. Their results show that estimates of ICC are associated with the prevalence of the outcome of interest, the nature of the outcome of interest (mortality or behavioural) and the size and number of clusters. They advise that when planning future trials, published estimates of ICCs from larger clusters are probably safer to use and a range of possible ICCs should be used for sample size calculations.

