Given the above mentioned ICCs for neonatal mortality, the formula to correct for clustering $[1 + (n-1) * ICC]$ with $n = 250$ (i.e. average cluster size) gives a required sample size for the IRIS study of 14,547 (ICC 0.0003) to 20,304 (ICC 0.002). For two reasons we expect the ICC in the IRIS study to be much more similar to 0.0003 than to 0.002. Our first argument is that the ICCs reported in the paper of Pagel et al. (2011) are based on prevalence rates ranging from 1.5% to 5.9% which is higher than the expected severe perinatal outcome in the IRIS study. As ICCs are associated with the prevalence of the outcome of interest [Pagel et al., 2011] we may expect the ICC in the IRIS study to be even lower than 0.0003. Our second argument is that midwife practices will offer both the control strategy (i.e. US on indication) and, later on, the intervention strategy (i.e. routine US). This will reduce the variation in characteristics and practice management between the intervention and control strategy group and thereby lower the size of the ICC .

Taking into account an ICC of 0.0003, the required sample size is 14,547 women. As not all women who will sign the informed consent form may receive care in the participating midwifery practice at the start of the third trimester, we adjusted this figure to a total of 15,000.

Effectiveness analyses

Firstly, we will assess the similarity between baseline characteristics of women having had the intervention strategy and women having had the control strategy. Secondly, we will compare baseline characteristics of drop-outs and completers by using logistic regression analysis. Thirdly, we will use multivariable logistic multilevel analyses to investigate the effect of routine US screening on perinatal outcome, adjusting for possible clustering of observations and confounders (e.g. ethnicity, maternal age, weight and height, smoking, alcohol use, drug use, blood pressure). We will base our analyses on intention to treat and set the level of significance at $p < 0.05$.

We will perform a subgroup analysis for women without US indication and for nulliparous women.

In addition to the intention to treat analysis we will also perform a per-protocol analysis, restricted to the women in the intervention group who received the two US examinations and to the women in the control group who did not receive any screening US.

Cost-effectiveness and cost-utility analyses

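### The prevalence argument for planning on the lowest borrowed ICC (0.0003) is contradicted by the protocol's own 1.54%, and the crossover argument is mis-stated, so the 80% power is conditional on an ICC that has not been supported

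*Protocol*

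**What the plan says.** All of this is in the Protocol, Statistical analyses, Sample size of full trial, unless another place is named.

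- The section states that "the expected rate of severe adverse perinatal outcome in the study population is 1.54" per cent, and the study group "agreed to strive for a reduction from 1.54% to 1.0% in the primary outcome".
- Before clustering: "With 80% power and a significance level of 0.05, we need to include 13,536 women".
- For the ICC it turns to five community-based cluster trials in low-income countries; "they present five ICCs for neonatal mortality ranging from 0.0003 to 0.002". It also reports those authors' advice that "a range of possible ICCs should be used for sample size calculations".
- It applies a design effect of 1 + (n−1) × ICC with n = 250 and prints 14,547 women at 0.0003 and 20,304 at 0.002.
- It then gives two reasons for expecting a value close to 0.0003. The first is that the source ICCs are "based on prevalence rates ranging from 1.5% to 5.9% which is higher than the expected severe perinatal outcome in the IRIS study", from which it concludes that "we may expect the ICC in the IRIS study to be even lower than 0.0003". The second is that each practice delivers both strategies, which is said to make the ICC smaller.
- It adopts 0.0003 and 14,547 women, raised to 15,000 because some consenting women may have left the practice's care by the third trimester. The summary gives the result as "A total of 15,000 women in 60 midwifery practices; 7,500 women per strategy".

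**The concern.** The ICC is the only step between 13,536 and 14,547. The benchmark is for a different endpoint and setting from the Dutch composite, so the choice within its range rests on the two stated reasons.

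The first can be checked against the section's own figures and fails: 1.54% is not below a range that starts at 1.5%. The second confuses two quantities. Crossing over does not change how alike women in one practice are. It changes how much that likeness affects the comparison of strategies. The formula used is the parallel-cluster one, in which crossing over has no part.

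At stake is how a null result is read. A reader would take 80% power at about 15,000 women as established, when it is conditional on the most favourable of five benchmark values.

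**Working it through.** **Inputs.** Rates 1.54% and 1.0% (difference 0.0054, mean 1.27%); alpha 0.05, power 80%, equal allocation, n = 250, ICC 0.0003 to 0.002, all from the protocol. Sidedness is not stated; two-sided is assumed because it reproduces the plan's figure.

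**1. Unadjusted size.** Per arm, [1.96 × √(2 × 0.0127 × 0.9873) + 0.8416 × √(0.0154 × 0.9846 + 0.01 × 0.99)]² / 0.0054² = 6,749, so 13,498 in total against 13,536 stated (0.3% apart). One-sided would give 10,632.

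**2. Clustering.** 13,536 × (1 + 249 × 0.0003) = 13,536 × 1.0747 = 14,547, as printed. 13,536 × (1 + 249 × 0.002) = 13,536 × 1.498 = 20,277, against 20,304 printed. The printed figure is exactly 13,536 × 1.5, so n was used there in place of n−1.

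**3. The comparison of prevalences.** 1.5% < 1.54% < 5.9%. The trial's rate is inside the range.

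**4. What prevalence could imply.** Assume a constant coefficient of variation, so that the ICC is proportional to p/(1−p). The protocol does not say which ICC goes with which prevalence, so both ends are shown for the value 0.002, moved to 1.54%:
- if seen at 1.5%: 0.002 × 0.015641 / 0.015228 = 0.0021
- if seen at 5.9%: 0.002 × 0.015641 / 0.062699 = 0.0005

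At the mean rate of 1.27% the two results are 0.0017 and 0.0004.

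**5. Power on the plan's formula.** The women per arm are divided by the design effect and put into the step 1 formula solved for power.

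| ICC | Design effect | N for 80% | Power, 15,000 analysed | Power, 14,547 analysed |
|---|---|---|---|---|
| 0.0003 | 1.0747 | 14,547 | 81.3% | 80.1% |
| 0.0005 | 1.1245 | 15,221 | 79.5% | 78.3% |
| 0.001 | 1.249 | 16,906 | 75.3% | 74.0% |
| 0.002 | 1.498 | 20,277 | 67.5% | 66.1% |

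The last column is shown because the extra 453 women (15,000 − 14,547) are the plan's allowance for women leaving care. The largest ICC that fits is (15,000/13,536 − 1)/249 = 0.00043 with 15,000 analysed, and (14,547/13,536 − 1)/249 = 0.00030 with 14,547.

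**6. Sensitivity to the ICC in the actual layout.** Study design describes 60 practices and 20 crossing every three months. Assumptions: four equal periods, 250/4 = 62.5 women per practice and period, a linear mixed model with a practice random effect, total variance 0.0127 × 0.9873 = 0.012539. Write τ² = ICC × 0.012539, σ² = (1 − ICC) × 0.012539/62.5 and c = τ²/(σ² + 4τ²). Power is Φ(0.0054/SE − 1.96).
- Without period terms, the variance of the effect is σ²/(60 − 40c). Power is 83.6%, 82.8% and 81.9% at ICC 0.0003, 0.001 and 0.002.
- With period terms, it is 60σ²(σ² + 4τ²)/(1600σ² + 4000τ²). Power is 49%, 47% and 45%.

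In both models the whole ICC range moves power by about 2 to 4 points, against 14 points on the plan's formula.

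**The case against.** **The slip is small.** The gap is 0.04 points against a bound printed to one decimal, the mean of the two assumed rates (1.27%) is below the whole range, and the operative claim is only that the ICC is nearer 0.0003 than 0.002. This stands in part: a value towards the low end remains arguable. It does not rescue the inference to a value below 0.0003, which was drawn from a comparison that is false as stated and needs a pairing of ICCs with prevalences that the protocol does not give.

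**The formula does deliver 80%.** A reader might infer that 80% power fails even on the plan's own formula. It does not: at 0.0003 the formula reproduces 14,547 and gives at least 80%. What lacks support is the input.

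**The range was disclosed.** The section prints the sample size at both ends and says openly where the ICCs come from. That is true, and choosing within a disclosed range is a judgement. But the reasons given for the choice have to hold.

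**The formula does not describe this trial.** This is the strongest objection, and it stands. Every practice delivers both strategies, so the within-practice comparison removes most of the ICC's influence (step 6). It limits the point to the stated figure and its stated basis. It also shows that the second argument has a sound core: the within-practice comparison is a real advantage, wrongly described as a lower ICC.

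**Conclusion.** The point holds in limited form. The prevalence comparison is false on the protocol's own figures, and the inference to an ICC below 0.0003 has no basis there. The second argument names the wrong mechanism and is not reflected in the formula. On that formula the 80% is conditional on an ICC of at most about 0.0003 to 0.0004, according to whether 14,547 or 15,000 women are analysed, and falls to about 67% at 0.002 with 15,000.

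Two stronger conclusions are not supported. One is that the true ICC is near 0.002: rescaling that value gives anything from about 0.0005 to 0.0021, and the protocol does not allow a choice between them. The other is that the trial's real power is 75% or 67%: those figures belong to a parallel-cluster formula. In the layout described, under the step 6 assumptions, the level depends far more on whether period terms are in the model than on the ICC. The Effectiveness analyses section names clustering and confounders and no period term. Whether period should be included is a separate question that this point does not settle.

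**What to change.** In Sample size of full trial:

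1. Delete the comparison of the source prevalences with the trial's rate, and the inference to an ICC below 0.0003.
2. Reword the second argument rather than delete it: offering both strategies in each practice leaves the ICC unchanged but reduces how much between-practice variation enters the treatment contrast, and the design-effect formula takes no credit for this.
3. State that, on the parallel-cluster formula, 80% power is conditional on an ICC up to about 0.0003 (14,547 analysed) to 0.0004 (15,000 analysed). If 81%, 75% and 67% at 0.0003, 0.001 and 0.002 are shown, label them as values from that formula only.
4. Restate the power of the fixed 15,000 women over the quoted ICC range with a calculation that matches the stepped wedge layout and the planned model.
5. Correct 20,304 to 20,277. This is minor, since that figure does not feed the final sample size.

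The cost is a wording change and one power calculation. No extra women and no design change are needed. The stated power becomes conditional.

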The IRIS study is designed as a stepped wedge cluster randomised trial (c-RCT, Figure 1). A stepped wedge design is a type of crossover design in which different clusters cross over (switch treatments) at different time points. Clusters cross over in one direction only; typically from control to intervention. The time at which a cluster starts with the intervention is randomized; more than one cluster may start the intervention at a particular time point [Hussey 2007]. The advantages of a stepped wedge design are: a) all practices will offer the intervention for a shorter or longer period of time, which may encourage them to take part, b) practices will serve as their own control for a variable time period which will reduce the variation in characteristics and practice management between the intervention and control strategy group. Note: in contrast to many other stepped wedge c-RCTs the women participating in our study will receive the intervention strategy OR control strategy.

Midwifery practice will be the unit of randomisation. Randomisation per practice rather than per midwife or client has the advantage of minimising contamination and therefore maximising contrast between the intervention and control strategy group.

All midwifery practices (n=60) will start in the control strategy and provide obstetric care as usual. At intervals of 3 months, 33,3% of all practices (n=20) will change status from control to intervention group and will start offering the intervention, i.e. routine biometry ultrasound in the third trimester of pregnancy. To balance the number of women in the intervention and control group, practices will be stratified prior to randomisation in large and small practices, with the average practice size as the cut-

off point (i.e. 250 clients a year). Within these two strata, a computer-generated random sequence will determine the order in which practices move from control to intervention status. This randomisation will take place after practices have been recruited for participation in the study and before data collection begins.

Figure 1: The IRIS stepped wedge design | UC = control strategy; INT= intervention strategy; US= ultrasonography

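### The sample size allows nothing for calendar period: once period is adjusted for, 15,000 women give about 45-49% power for 1.54% vs 1.0%, not 80%

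*Protocol*

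**What the plan says.** Under Statistical analyses, Sample size of full trial, the protocol gives the control rate ("Based on PRN data the expected rate of severe adverse perinatal outcome in the study population is 1.54" %) and the target ("The IRIS study group agreed to strive for a reduction from 1.54% to 1.0% in the primary outcome"). It then states: "With 80% power and a significance level of 0.05, we need to include 13,536 women". To allow for clustering it applies "the formula to correct for clustering $[1 + (n-1) * ICC]$ with $n = 250$ (i.e. average cluster size"). The ICC range comes from a published set of community cluster trials: "In their paper they present five ICCs for neonatal mortality ranging from 0.0003 to 0.002". It settles on the low end ("Taking into account an ICC of 0.0003, the required sample size is 14,547 women") and rounds up to 15,000 to cover women who leave the practice before the third trimester.

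The design is set out under Study design. All 60 practices start in control, and "At intervals of 3 months, 33,3% of all practices (n=20) will change status from control to intervention group". Recruitment runs over months 1-12, and the summary gives 7,500 women per strategy.

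Under Effectiveness analyses, the primary model is a multilevel logistic regression that adjusts for clustering and for an open list of maternal characteristics. Calendar time is not on that list.

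**The concern.** The factor 1 + (n-1) x ICC belongs to a trial in which each practice stays in one arm and both arms run side by side. Here every practice moves from control to intervention at one of three dates. The first quarter is all control and the last is all intervention, so neither contains a concurrent comparison. Averaged over the layout, intervention women are recruited 5 months later than control women (mean 8.5 vs 3.5 months).

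An analysis that separates the strategy effect from time pays for this in variance, and the sample size does not budget for that cost. An analysis that ignores time keeps its power but attributes any background change to the intervention. The protocol gives reason to expect such change: its problem definition says third trimester scanning is spreading as routine, and the IRIS-study section warns that it may soon be common practice. The same text faults earlier trials as underpowered and presents this one as large enough, so the power figure matters.

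**Working it through.** **Inputs.** From the protocol: rates 1.54% and 1.0%; alpha 0.05 (two-sided reproduces the stated size); 80% power; ICC 0.0003 to 0.002; 60 practices; 15,000 women; three steps of 20 practices at 3-month intervals; 12 months of recruitment. Assumed: four equal periods and equal practices, hence 15,000/(60 x 4) = 62.5 women per practice per period. The design figure is not shown, but the text implies this layout and it matches the stated allocation: the mean of 0, 1/3, 2/3, 1 is 1/2, or 7,500 per strategy.

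**1. The protocol's own figures.** A two-proportion calculation without continuity correction gives 6,749 per arm, 13,498 in total (stated 13,536). Then 13,536 x (1 + 249 x 0.0003) = 14,547, exactly as stated. At ICC 0.002, 13,536 x (1 + 249 x 0.002) = 20,277 (stated 20,304, which is 13,536 x (1 + 250 x 0.002)). By this formula, power at 15,000 is 81% at ICC 0.0003 and 67% at ICC 0.002. The arithmetic is sound for a parallel cluster trial.

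**2. Cost of period adjustment at ICC = 0.** The overall variance of the strategy indicator is 1/2 x 1/2 = 1/4. Within periods it is 0, 2/9, 2/9, 0, with mean 1/9. The variance factor is (1/4)/(1/9) = 2.25. Clustering plays no part in this.

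**3. With clustering.** The stepped-wedge design effect for k = 3 steps and n = 62.5, one baseline and one post-step period each, times 4 periods, is

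4 x [1 + ICC(4n - 1)] / [1 + ICC(2.5n - 1)] x 3(1 - ICC) / [2(3 - 1/3)].

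- ICC 0.0003: 4 x (1.0747/1.0466) x 0.5623 = 2.31
- ICC 0.002: 4 x (1.498/1.3105) x 0.5614 = 2.57

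Weighted least squares with fixed period effects and a random practice effect gives the same factors. The protocol used 1.07.

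**4. Power at 15,000.** With mean rate 1.27%, the unadjusted standard error of the difference is sqrt(4 x 0.0127 x 0.9873/15,000) = 0.183 percentage points. Multiply by the square root of the factor; power is Phi(0.54/SE - 1.96).

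| ICC | Factor | Effective N | SE (points) | Power, period adjusted | Power, no time term |
|---|---|---|---|---|---|
| 0 | 2.25 | 6,667 | 0.274 | 50% | 84% |
| 0.0003 | 2.31 | 6,494 | 0.278 | 49% | 84% |
| 0.002 | 2.57 | 5,844 | 0.293 | 45% | 82% |

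Cross-checks agree. Logistic information with period indicators and no clustering gives 49.9%. A linear time term at ICC 0.0003 gives 49.3%. A simulation of 1,500 trials at ICC 0.0003 gives 51.5% with period terms (Monte Carlo error about 1.3 points) and 82.9% without.

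**5. What 15,000 can detect with 80% power.** A fall from 1.54% to about 0.79% at ICC 0.0003 (0.75/1.54 = 49% relative) or 0.76% at ICC 0.002 (0.78/1.54 = 51%). The target is 0.54/1.54 = 35%.

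**6. Women needed for 80% power at the target.** Keeping 60 practices and enlarging them: about 32,000 (ICC 0.0003) to 38,400 (ICC 0.002). Adding practices of 250 women: 13,536 x 2.31, about 31,300, to 13,536 x 2.57, about 34,700.

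**The case against.** The strongest reply is that the protocol is consistent with the model it names. That model lists clustering and maternal confounders but not calendar time, and without a time term power is 82-84%. Moving to a stepped-wedge formula would not by itself lower power; only period adjustment does. A separate analysis plan may exist, and the confounder list is open-ended.

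This stands to the following extent. A reader might infer that the protocol's arithmetic is wrong, or that power is 45-49% under any analysis. The documents support neither: the arithmetic reproduces, and the 45-49% is conditional on adjusting for period. The reply does not rescue the claim, however. If period is adjusted for, the sample size has not allowed for it. If it is not, the 80% depends on there being no time trend, against the protocol's own account of changing practice.

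A second reply is that practices act as their own controls and the ICC is probably very low. The random practice effect already credits the first, and power is only 50% at ICC 0, so a low ICC does not help.

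A reader might also infer that a non-significant result can never rule out the target. That goes too far. The 95% half-width is about 1.96 x 0.278 = 0.545 points at ICC 0.0003, so a non-significant estimate only slightly in the unfavourable direction would already exclude a 0.54-point reduction. Nor do the documents show that a null result would be reported as no benefit.

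**Conclusion.** The point holds in conditional form. The protocol describes a stepped wedge but sizes it with a parallel-cluster factor that has no term for time. Under period adjustment the chance of detecting the stated target is about even or slightly worse, against the 80% claimed. The result rests on four equal periods and equal practice sizes, and on the protocol's own ICC range. It hardly depends on the ICC, because nearly all the loss comes from the overlap of strategy with calendar time. This should be corrected, since it concerns the headline power for the primary clinical outcome.

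A minor point sits in the same paragraph. The low ICC is defended by saying the source trials had "prevalence rates ranging from 1.5% to 5.9% which is higher than the expected severe perinatal outcome in the IRIS study", but 1.54% lies inside 1.5%-5.9%, just above its lower edge. The argument fails as written, though removing it does not change the conclusion.

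**What to change.** 1. In Sample size of full trial, replace the design-effect paragraph with a stepped-wedge calculation that includes period effects. State power at 15,000 as about 45-49% over ICC 0.002 to 0.0003, with 80% power only for a reduction to about 0.79% (ICC 0.0003) or 0.76% (ICC 0.002), and state the assumptions of equal periods and practice sizes.
2. If a size for 80% power is quoted, give its basis: about 32,000 to 38,400 women with 60 practices, or about 31,000 to 35,000 with practices added at 250 women each.
3. In Effectiveness analyses, add calendar period as a fixed effect to the primary multilevel logistic model, so that sample size and analysis agree.
4. State that a non-significant result will be interpreted from its confidence interval against the 1.54% to 1.0% target.
5. Delete the argument that the source prevalences exceed the IRIS rate.

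The cost is one rewritten paragraph, one model term and one sentence on interpretation. The real downside is that the stated power becomes less favourable.
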